9.2.2. Adverse Events Based on Signs and Symptoms

When collecting AEs, the recording of diagnoses is preferred (when possible) rather than recording a list of signs and symptoms, for example: congestive heart failure rather than low ejection fraction. However, if a diagnosis is known and there are other signs or symptoms that are not generally part of the diagnosis, the diagnosis and each sign or symptom not part of the diagnosis will be recorded separately, for example: congestive heart failure and conjunctivitis.

9.2.3. Adverse Events Based on Examinations and Tests

If lab values are judged as clinically significant and/or a treatment has been given, they will be captured as AEs and if SAE criteria are fulfilled they will also be SAEs.

If vital signs are judged as clinically significant and/or require a treatment, then they will be captured as AEs and if SAE criteria are fulfilled they will also be SAEs.

Any new or aggravated clinically relevant abnormal medical finding at a physical examination as compared with the baseline assessment will be reported as an AE and if SAE criteria are fulfilled they will also be SAEs.

Wherever possible the reporting investigator uses the clinical, rather than the laboratory term (e.g., anaemia *versus* low haemoglobin value).

9.2.4. Follow-up of Unresolved Adverse Events

Any AEs that are unresolved at the subject's last AE assessment in the study are followed up by the investigator until stabilization, for as long as medically indicated or the overall clinical outcome of the subject is known, unless the subject is documented as "lost to follow-up". All SAEs and AEs leading to discontinuation should be followed until the event resolves or stabilizes.

Reasonable attempts to obtain this information must be made and documented. Hansa Biopharma retains the right to request additional information for any subject with ongoing AE(s)/SAE(s) at the end of the study, if judged necessary.

9.2.5. Reporting of Serious Adverse Events

All SAEs have to be reported, whether or not considered related to the investigational product, or to the study procedure(s), on a separate SAE form. In the AE form, it will be added that the AE is considered serious. SAEs will be recorded from the time of informed consent.

An assigned contract research organisation (Primevigilance) will be responsible for reporting all SAEs to RAs in accordance with ICH GCP and local regulations. Hansa Biopharma or the study monitor will be responsible for reporting to IECs/IRBs.

As soon as the investigator is aware of a potential SAE he/she should contact Primevigilance by e-mail and no later than 24 hours after the knowledge of such a case. At the time of initial reporting the investigator must provide as a minimum requirement, subject number, birth date, description of the SAE and a preliminary assessment of causality.

Contact Information to Primevigilance:

For fatal or life-threatening AEs where important or relevant information is missing, active follow-up is undertaken immediately. Investigators or other site personnel inform Hansa Biopharma, the monitor, and Primevigilance of any follow-up information on a previously reported SAE immediately but no later than within 24 hours of when he or she becomes aware of it. The monitor or Hansa Biopharma will advise the investigator/study site personnel how to proceed.

The SAE reporting procedures are detailed in the study specific Safety Management Plan. This plan is an agreement between Hansa Biopharma and Primevigilance.

9.2.6. Reporting of Suspected Unexpected Serious Adverse Reactions

SUSARs must be reported to RAs. A suspected serious adverse reaction is any SAE for which there is a reasonable possibility that the investigational product caused the AE. A serious adverse reaction is considered "unexpected" if it is not listed in the reference safety information section of the investigator brochure or is not listed at the specificity or severity that has been observed.

SUSARs with an outcome of death or which are life threatening must be reported to the relevant RAs within 7 calendar days, all other SUSARs must be submitted within 15 calendar days. The SUSAR reporting procedures are detailed in the study Safety Management Plan. This plan is an agreement between Hansa Biopharma and Primevigilance. Hansa Biopharma will notify the appropriate RA(s) and all participating study investigators of any SUSARs on an expedited basis and in accordance with applicable regulations. In addition, Hansa Biopharma is

responsible for informing all investigators in all other ongoing studies involving imlifidase about all SUSARs.

It is the responsibility of the site investigator to promptly notify the IEC/IRB and other appropriate institutional regulatory bodies of all SUSARs received involving risk to human subjects as per their applicable requirements.

9.3. Pregnancy and Pregnancy Outcome

Pregnancy is an exclusion criterion and a pregnancy test is performed at the screening visit and at the last study visit.

If a subject becomes pregnant during the follow up phase of the study, the subject will continue in the study according to study protocol, if possible. A Pregnancy Report Form must be sent by the investigator to Primevigilance at the latest within two weeks of learning of the pregnancy. The outcome of all pregnancies (spontaneous miscarriage, elective termination, normal birth or congenital abnormality) will be followed up on the Pregnancy Report Form even after the subject has completed or discontinued the study. Primevigilance will follow up on pregnancy outcome 4 weeks after the projected due date.

Pregnancy itself is not considered an AE or SAE, but any event occurring during pregnancy that meets serious criteria must be reported to Hansa Biopharma and will be handled as a SAE. Spontaneous abortions, congenital abnormalities/birth defects are always considered to be SAEs and will be reported and followed up in accordance with other SAEs. Any SAE occurring as a result of a post-study pregnancy and considered reasonably related to the study drug by the investigator will be reported to Hansa Biopharma (or designee).

10. STUDY MANAGEMENT

10.1. Pre-study Activities

Before the first subject is enrolled into the study, it may be necessary for a representative of Hansa Biopharma to visit the investigational study site for a pre-study visit to:

- Determine the adequacy of the facilities to give Hansa Biopharma information about whether the study centre has knowledge, enough time, a sufficient subject pool, and sufficient training to manage the study in a good way in terms of subject inclusion, subject handling, data and overall study management.
- Discuss with the investigator(s) (and other personnel involved with the study) their responsibilities with regard to protocol adherence and the responsibilities of Hansa Biopharma or its representatives.

Before the first subject is entered into the study, a Hansa Biopharma representative will review and discuss the requirements of the clinical study protocol and related documents with the investigational staff and also train them in any study specific procedures and system(s) utilized at a site initiation visit.

The principal investigator will ensure that appropriate training relevant to the study is given to all staff, and that any new information relevant to the performance of this study is forwarded to the staff involved.

The principal investigator will maintain a record of all individuals involved in the study (medical, nursing and other staff).

10.2. Monitoring of the Study

During the study, a Hansa Biopharma representative will have regular contacts with the study site, including visits to:

- Provide information and support to the investigator(s).
- Confirm that facilities remain acceptable.
- Confirm that the investigational team is adhering to the protocol, ICH GCP, data are being accurately and timely recorded in the CRFs, and IMP accountability checks are being performed.
- Perform SDV (a comparison of the data in the CRFs with the subject's medical records at the hospital or practice, and other records relevant to the study) including verification of informed consent of participating subjects.
- If a subject withdraws informed consent to the use of their biological samples; ensure this is reported to Hansa Biopharma and biological samples are identified, disposed/destroyed accordingly, and the action is documented, and reported to the subject.

Hansa Biopharma and its representatives will be available between visits if the investigator(s) or other staff at the centre need information and advice about the study conduct. Details about monitoring are specified in a study specific monitoring plan.

10.3. Source Data

Source data is defined in ICH GCP. Except for SAEs, which must always be source data verified, the extent to which SDV will be carried out must be decided, specified and detailed in the Monitoring Plan. For all data recorded, the source document must be defined in a source document agreement at each study site. There must only be one source defined at any time for any data elements. Source data for randomization will be located in the eCRF.

10.4. Audit and Inspection

The investigator will make all the study-related source data and records available at any time to Quality Assurance auditor(s) mandated by Hansa Biopharma, or to domestic/foreign regulatory inspectors or representatives from IECs/IRBs who may audit/inspect the study.

The main purposes of an audit or inspection are to assess compliance with the study protocol and the principles of ICH GCP and all other relevant regulations.

The subjects must be informed by the investigator and in the Informed Consent Documents that authorised Hansa Biopharma representatives and representatives from RAs and IECs/IRBs may wish to inspect their medical records. During audits/inspections the auditors/inspectors may copy relevant parts of the medical records. No personal identification apart from the screening/randomisation number will appear on these copies.

The investigator should notify Hansa Biopharma without any delay of any inspection by a RA or IEC/IRB.

10.5. Study Agreements

The principal investigator must comply with all the terms, conditions, and obligations of the clinical study agreement for this study. In the event of any inconsistency between this clinical study protocol and the clinical study agreement, the clinical study protocol will prevail.

Agreements between Hansa Biopharma and the principal investigator must be in place before any study-related procedures can take place, or subjects be enrolled.

11. DATA MANAGEMENT

11.1. Case Report Form

An eCRF system provided by a CRO will be used for data capture. The system is validated and access at all levels to the system is granted/revoked following Hansa Biopharma and vendor procedures, in accordance with regulatory and system requirements.

After the study database is declared clean and released to the statistician, a final copy of the database will be stored at Hansa Biopharma. The investigator will also receive a copy of the study site's final and locked data (including audit trail, meta-data and queries) as write-protected PDF-files produced by the CRO. The PDF-files will be stored on a CD/DVD and will be provided to the investigator before access to the eCRF is revoked.

11.2. Provider of Data Management

All data management procedures will be outsourced to a CRO. Activities will be specified in a Data Management Plan prepared by the CRO and reviewed and approved by Hansa Biopharma. The plan will be issued before data collection begins and will describe all functions, processes and specifications for data collection, cleaning and validation.

11.3. Coding

For medical coding of AEs, medical/surgical history, including transplantation history, and concomitant medication the most recent versions of the Medical Dictionary for Regulatory Activities (MedDRA) and WHO Drug will be used at study closure (unless decided otherwise by Hansa Biopharma).

The coding will be outsourced to a CRO. All coding performed will be approved by Hansa Biopharma prior to study closure/database lock.

11.4. Handling of External Data

Handling of external data received by Hansa Biopharma from vendors will be performed in a secure environment and according to a pre-defined Data Transfer Specification.

12. STATISTICAL METHODS

The statistical analyses will be outsourced to a CRO. Prior to clean file, a Statistical Analysis Plan (SAP) with details on statistical analysis and data presentation will be established. No formal statistical hypothesis testing will be performed in this study.

Summary tables will in general be presented by treatment and total unless this is not appropriate for specific tables. Mean figures will similarly be presented by treatment.

Summary statistics for continuous variables will in general be presented as n, arithmetic mean, standard deviation, median, minimum and maximum. When continuous data are recorded at different time points absolute values at each time point and, if relevant, changes from baseline may be presented.

For categorical data frequencies and percentages will be presented.

Due to the exploratory nature of the study, missing data will remain missing and no adjustment will be implemented.

12.1. Analysis Sets

All enrolled and treated subjects will qualify for the Full Analysis Set (FAS), the Per Protocol Analysis Set (PPS), the Safety Analysis Set and the Pharmacokinetic Analysis Set (PKS). The decision to exclude subjects from any of the analysis sets will be taken by the clinical study team before database lock and documented in the database lock minutes. Further details will be specified in the SAP.

12.1.1. Full Analysis Set

The FAS will include all treated subjects for whom relevant post baseline efficacy and safety data have been collected.

12.1.2. Per Protocol Analysis Set

The PPS will include all subjects in the FAS who are not excluded because of important non-compliance that will affect the efficacy data such as admission criteria, protocol deviations or other non-compliance.

12.1.3. Safety Analysis Set

The safety analysis set comprises all treated subjects.

12.1.4. Pharmacokinetic Analysis Set

The PKS will be defined by the PK analyst taking admission criteria, protocol deviations and other non-compliance into consideration.

12.2. Subject characteristics

The demographics and other baseline characteristics will be summarised and listed using descriptive techniques.

12.2.1. Subject disposition

The subject disposition will present number of subjects as enrolled, completed, withdrawn overall and by reason for withdrawal and finally by each of the analysis set.

12.2.2. Demographics and Other Baseline Characteristics

The subject's demographics and other baseline characteristics will be summarised and listed.

12.2.3. Recent and Concomitant Medication

Recent and concomitant medication will be summarised by anatomical therapeutic chemical (ATC) code. In addition, listings with ATC code and generic drug name will be prepared.

12.2.4. Exposure and Compliance

Exposure will be tabulated and listed.

12.3. Statistical Analysis of Endpoints

12.3.1. Primary efficacy endpoint

The primary endpoint is the maximum reduction in DSA (MFI sum for relevant DSAs) at any time point during the 5 days following the start of treatment. A subject will have at least one DSA and a DSA is considered relevant if it is at least 1000 MFI pre-dose. The reduction is derived as follows:

- 1) Calculate the reduction (%) in sum of DSAs as $100 \times (DSA_0 - DSA_t) / DSA_0$ for each subject and time point. Only DSAs with a pre-dose MFI of 1000 or more will be included in the calculations
- 2) Find the time point with maximum reduction within 5 days for each subject
- 3) The maximum reduction per subject will give a single value as the primary endpoint for the subject

Where DSA_t is the analysis result in total MFI for relevant DSAs at time t.

Due to the exploratory nature of this study, no formal hypothesis will be tested. The difference in reduction between the two treatments will be presented with 95% CI. Each subject will be given equal weight in the calculation of the treatment difference irrespective of number of DSAs for the subjects.

A summary table showing the proportion of reduction of DSAs calculated per subject will also be presented.

12.3.2. Reduction of total serum IgG

The total serum IgG is measured by the PD assay. A binary endpoint is defined as 'Yes' if the subject minimum IgG value at any timepoint during the 5 days following the start of treatment is less than 5% of baseline. The proportion of subjects with a positive reduction will be summarized in a table. The difference in proportion between treatments will be presented with a 95% CI.

12.3.3. Detectable intact IgG on a Western blot

An endpoint is defined as reached for a subject if no detectable intact IgG is found by the SDS-PAGE/Western blot assay at any time point over 180 days following treatment. The proportion of subjects who reached the endpoint will be summarized in a table. The difference in proportion between treatments will be presented with a 95% CI.

12.3.4. Donor specific antibodies (DSA)

DSAs will be measured using HLA-SAB assay and a functional assay e.g. C1q or C3d assay. MFI levels will be listed per subject and time point. Spaghetti plots will show the DSA level versus time for each subject. A mean plot by treatment and time point will be presented.

Finally, a listing with all DSA by subject and time point will be prepared.

In addition, subject listings of MFI values for all HLA will be presented.

12.3.5. Kidney function

The kidney function will be evaluated by the parameters eGFR, P-creatinine and albumin/creatinine ratio in urine and biopsies. The laboratory parameters will be summarised as part of the safety data tabulation. Derivation of eGFR will be detailed in the SAP.

Kidney biopsies will be assessed according to the Banff (2017) criteria pre-dose and at day 29 and 180. The biopsy data will be summarised by treatment and listed. In addition, [REDACTED] will be summarised.

12.3.6. Signs of transplant glomerulopathy 180 days post treatment

Possible transplant glomerulopathy 180 days post treatment will be tabulated by treatment and presented by listings.

12.3.7. Number of sessions with PE for 180 days

The number of PE sessions for 180 days will be summarized by treatment and listed.

12.3.8. Number of patients with resolution of AMR at day 180

The number of patients with resolution of AMR at day 180 will be tabulated by treatment and listed.

12.3.9. The number of patients with graft failure at day 180

The number of patients with graft failure at day 180 will be summarized by treatment and listed.

12.3.10. Patient survival at day 180

The patient survival on day 180 will be tabulated and listed.

12.3.11. Pharmacokinetic

Imlifidase concentrations will be summarised by time point for the imlifidase treatment group and presented as spaghetti plots and mean plots.

PK variables (C_{max} , T_{max} , $t_{1/2}$, AUC, CL, and V) are calculated and will be summarized using n, arithmetic and geometric mean, standard deviation, coefficient of variation (CV), minimum, median, and maximum. For the terminal half life, the harmonic mean will also be presented.

12.3.12. Pharmacodynamics

Pharmacodynamics data (total serum IgG) will be summarized by time point. In addition, data on total serum IgG will be presented by mean and spaghetti plots. Finally, data will be listed. SDS PAGE and Western blot results will be presented by time point.

12.3.13. Analysis of Adverse Events

AEs will be coded according to the latest version of the MedDRA. All data will be listed by patient. Only treatment emergent AEs will be presented in summary tables. Separate data listing will be provided for AEs that are defined as pre-treatment or post-treatment emergent.

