- Change from baseline (at screening) in mRNA levels in kidney biopsies evaluated [REDACTED] at 29 and 180 days from baseline. If kidney biopsy is performed before screening, mRNA levels will be evaluated on day 29 and day 180 (no baseline will be available)
- Safety parameters (AEs, safety laboratory tests, vital signs and ECG)
- Type, frequency and intensity of adverse events
- Number of sessions with PE
- Total Serum IgG levels over time
- Presence of intact IgG on SDS-page/Western blot until start of IVIg treatment
- DSA functionality determined by C1q or C3d analysis pre- and post-treatment
- PK profile of imlifidase (C_{max} , T_{max} , $t_{1/2}$, AUC, CL, V)
- Presence of ADA (anti-implifidase IgG)

Methodology

This is a randomized, open label, multi-centre, active control study. The study will primarily examine the reduction in mean levels of DSA after treatment with imlifidase compared with PE in patients diagnosed with active or chronic active AMR according to Banff 2017 criteria, including presence of DSA(s). Included subjects will be randomized to receive either one dose of imlifidase 0.25 mg/kg or 5-10 sessions of PEs. All subjects will receive pulse methylprednisolone for three days, starting before the first treatment, followed by a tapering schedule with prednisolone/prednisone. Subjects will receive high dose IVIg 3 days after imlifidase treatment and directly after the last PE. A single dose of rituximab will be given 5 days after completed IVIg infusion.

Study Procedures/Assessments

Before inclusion into the study, a biopsy will be collected from all subjects, and assessments of DSA and ADA (IgE), vital signs, ECG as well as laboratory parameters including haematology, clinical chemistry, haemostasis, urinalysis, and PCR test for SARS-CoV-2 will take place. Subjects will be randomised to imlifidase infusion, 0.25 mg/kg over 15 min, or 5-10 PE treatment, and subsequently followed for 180 days after start of treatment. Blood samples for DSA, PK, PD and ADA will be collected at multiple time points during the study. Protocol biopsies will be performed on day 29 and on day 180 and kidney function will be followed by plasma or serum creatinine measurements, eGFR calculations and urine sample for measurement of albumin/creatinine ratio during the full study period.

Safety parameters will be assessed up to day 180. Reporting of adverse events will be done throughout the study.

Number of subjects

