5.2. Control treatment

The control treatment in this study is PE which is a treatment with no active substance and thus not an IMP. PE will be prepared and performed according to the standard of care at each site. 5-10 sessions of PE will be performed.

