5.3. Non-Investigational Medicinal Product(s)

Non-Investigational Medicinal Products (NIMPs) will be sourced from the investigational site pharmacy supply. Essential information about the NIMPs is to be found in the latest versions of respective Summary of Product Characteristics.

The subjects will be treated with the following NIMPs (other treatments may be used as required at the investigator's discretion):

Prophylactic antibiotic (all subjects):

All subjects will receive a standard regimen of antibiotics according to local clinical practice, starting before the first treatment and continuing until IgG levels return to acceptable values, as judged by the investigator.

Premedication (imlifidase arm):

All subjects in the imlifidase arm, will be given antihistamine (orally) as pretreatment before imlifidase infusion.

Treatment schedule for steroid dosing (all subjects):

Day 1: Methylprednisolone 500 mg as premedication before treatment
Day 2-3: Methylprednisolone 500 mg daily
Day 4: Prednisolone/prednisone 60 mg
Day 5: Prednisolone/prednisone 50 mg
Day 6: Prednisolone/prednisone 40 mg
Day 7: Prednisolone/prednisone 30 mg
Day 8: Prednisolone/prednisone 20 mg will continue daily for 1 week, followed by 10 mg daily for 1 week and thereafter 5 mg daily throughout the study

Treatment with IVIg (all subjects)

Imlifidase arm: subjects will be given a high dose of IVIg (2 g/kg BW, maximum of 140 g), on day 4 (may be given over 2 days, as judged by the investigator). If a subject in this arm has to be treated with PE for medical reasons, IVIg will be given after the last session of PE.

PE arm: a high dose of IVIg (2 g/kg BW, maximum of 140 g) will be given after the last session of PE (may be given over 2 days, as judged by the investigator).

Treatment with Rituximab (all subjects)

A single dose of rituximab, 375 mg/m², will be given to all subjects 5 days after completion of the IVIg infusion.

Rituximab requires use of contraception for 12 months after treatment. Women of childbearing potential will be encouraged to continue using highly effective contraceptive method for at least 6 months after end of study.

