12.3.13.2. Treatment Emergent Adverse Events

A treatment emergent adverse event is any adverse event occurring after the administration of the IMP and within the time of residual drug effect, or a pre-treatment adverse event or pre-existing medical condition that worsens in intensity after administration of the IMP and within the time of residual drug effect.

The time of residual drug effect is the estimated period after the administration of the IMP, where the effect of the product is still considered to be present based on pharmacokinetic, pharmacodynamic or other substance characteristics. The residual drug effect is generally accepted to be 5 times the terminal half-life. The terminal half-life of imlifidase is expected to be within the range of approx. 100 hours, i.e. in this study the residual drug effect is likely to be well within the 29 Day assessments. All AEs occurring up to Day 29 are regarded as treatment emergent.

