4.7.1 Adverse events

Adverse events (AEs) will be classified according to the latest effective version of MedDRA.

A treatment emergent adverse event (TEAE) is any adverse event occurring after the administration of the IMP and within the time of residual drug effect, or a pre-treatment adverse event or pre-existing medical condition that worsens in intensity after administration of the IMP and within the time of residual drug effect.

The time of residual drug effect is the estimated period after the administration of the IMP, where the effect of the product is still considered to be present based on pharmacokinetic, pharmacodynamic or other substance characteristics. The residual drug effect is generally accepted to be 5 times the terminal half-life. The terminal half-life of imlifidase is expected to be within the range of approx. 100 hours, i.e. in this study the residual drug effect is likely to be well within the 29 Day assessments. All AEs occurring up to Day 29 are regarded as treatment emergent.

An AE overview summary table will be prepared including the number of patients reporting an AE, the percentage of patients (%) with an AE, and the number of events (E) reported for the following categories:

- TEAEs
- Related TEAEs (TEAEs considered to be possibly or probably related to IMP as judged by the investigator)
- Related Serious TEAEs
- Deaths
- Treatment-emergent Serious Adverse Events (SAEs)
- TEAEs leading to withdrawal
- Severe and life-threatening AEs

Treatment-emergent AEs will be summarised in a table by dictionary level, i.e., System Organ Class (SOC) and Preferred Term (PT) for MedDRA. The table will display the total number of patients reporting a TEAE, the percentage of patients (%) with a TEAE and the number of events (E) reported. TEAEs will be presented by SOC sorted alphabetically and PT sorted in decreasing frequency of occurrence. For the summary tables the SAF set will be applied.

Summary tables will be prepared for:

- All TEAEs
- TEAEs by causality (related/unrelated)
- TEAEs by intensity
- Related TEAEs by intensity
- SAEs
- SAEs by causality (related/unrelated)
- Treatment-emergent SAEs
- Treatment-emergent SAEs by causality (related/unrelated)

- Treatment-emergent SAEs leading to death
- TEAEs leading to withdrawal

Data listings will be provided for:

- All TEAEs sorted by patient number
- All TEAEs sorted by MedDRA SOC and PT
- SAEs
- Treatment-emergent SAEs
- Treatment-emergent SAEs leading to death

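### Non-serious adverse events after Day 29 are listed but never tabulated by arm, because the table window follows imlifidase's half-life and not the 180-day follow-up

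*Protocol*

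**What the plan says.** Protocol 12.3.13 restricts tabulation: "Only treatment emergent AEs will be presented in summary tables". AEs before treatment or after the window go to separate listings.

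Protocol 12.3.13.2 sets the window from the drug's kinetics: "The residual drug effect is generally accepted to be 5 times the terminal half-life", and "The terminal half-life of imlifidase is expected to be within the range of approx. 100 hours". SAP 4.7.1 repeats this and concludes: "All AEs occurring up to Day 29 are regarded as treatment emergent". Neither document gives a reason based on PE, IVIg or rituximab.

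The window opens with the investigational product: "A treatment emergent adverse event is any adverse event occurring after the administration of the IMP and within the time of residual drug effect". Protocol 5.2, however, states: "The control treatment in this study is PE which is a treatment with no active substance and thus not an IMP".

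Follow-up is much longer than the window. The protocol synopsis says "Safety parameters will be assessed up to day 180", and Protocol 7.2.5 records AEs from consent to the end of the study. AE kind, frequency and severity are a secondary endpoint (Protocol 2.2.2, SAP 1.1.2), and comparing safety with PE is a secondary objective.

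SAP section 8 plans two tables that are not limited to treatment-emergent events: all SAEs (14.3.6) and all SAEs by causality (14.3.7). AEs after the window otherwise appear in listing 16.3.1.8.

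Both arms receive IVIg and rituximab. IVIg is on Day 4 in the imlifidase arm and after the last of 5 to 10 sessions in the PE arm. Under Protocol 5.3, rituximab "will be given to all subjects 5 days after completion of the IVIg infusion". SAP Table 3 gives 3 to 4 days for the PE arm.

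**The concern.** A window built on one drug's elimination is applied to a comparison of two regimens, both of which include further active treatments given later. This has two consequences.

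First, no planned table compares non-serious AEs between arms over most of the follow-up, although the study collects them and names them as a secondary endpoint. A reader of the report would have to count them from a listing.

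Second, the fixed Day 29 cut-off leaves less time after IVIg and rituximab in the PE arm whenever those treatments come later there. An event that follows rituximab by a given interval could then be tabulated in one arm and only listed in the other.

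**Working it through.** **1. The plan's own figure.** The inputs are a half-life of about 100 h and a multiple of 5 (Protocol 12.3.13.2). 5 x 100 = 500 h, and 500 / 24 = 20.8 days. With dosing on Day 1 this ends at about Day 21.8, inside Day 29 as the plan says. A half-life up to 28 x 24 / 5 = 134 h would still fit. The cut-off is therefore sound for imlifidase exposure.

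**2. Follow-up outside the tables.** 180 - 29 = 151 days, and 151 / 180 = 84%. I take the window to end on Day 29. Protocol 12.3.13.3 ends it at visit 8, which has a window of plus or minus 3 days.

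**3. Time after rituximab inside the window.** The inputs are IVIg given on one day or over two, and rituximab 5 days after completion (Protocol 5.3). In the PE arm IVIg starts on the last PE day (Protocol 1.2). The interval between sessions is not stated, so the spacings below are assumptions.

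- Imlifidase arm: IVIg ends Day 4-5, rituximab is on Day 9-10, and 29 - 9 = 20 or 29 - 10 = 19 days remain.
- PE arm: last session day L = 1 + (n - 1) x interval; rituximab on Day L + 5 or L + 6; days remaining = 29 minus that day.
- For equal IVIg duration, the shortfall against the imlifidase arm is L - 4 days.

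| PE schedule (assumed) | L | Rituximab day | Days left to Day 29 | Shortfall (days) |
|---|---|---|---|---|
| 5 daily | 5 | 10-11 | 18-19 | 1 |
| 10 daily | 10 | 15-16 | 13-14 | 6 |
| 5 on alternate days | 9 | 14-15 | 14-15 | 5 |
| 10 on alternate days | 19 | 24-25 | 4-5 | 15 |
| 5 every third day | 13 | 18-19 | 10-11 | 9 |
| 10 every third day | 28 | 33-34 | none | all 19-20 |

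The shortfall in time after IVIg start is also L - 4: 25 days remain in the imlifidase arm and 29 - L in the PE arm.

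**4. The other rituximab timing.** With SAP Table 3's 3 to 4 days and five daily sessions, rituximab falls on Day 8-10 and 19-21 days remain. The shortfall disappears.

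**5. Effect of tabulating to Day 180.** Take ten daily sessions, one-day IVIg and the 5-day gap. The PE arm's post-rituximab time is 14 / 20 = 70% of the imlifidase arm's at Day 29 and (180 - 15) / (180 - 9) = 165 / 171 = 96% at Day 180. With ten alternate-day sessions it is 5 / 20 = 25% and (180 - 24) / 171 = 156 / 171 = 91%.

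**The case against.** Several stronger readings are tempting, and the documents do not support them.

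- *Every AE table stops at Day 29.* It does not. Tables 14.3.6 and 14.3.7 cover all SAEs and stand apart from the treatment-emergent SAE tables 14.3.8 and 14.3.9. The overview rows for deaths and for severe or life-threatening AEs also carry no treatment-emergent label, although that table's title does. Laboratory values, vital signs, ECG, graft loss and survival are tabulated too.
- *The arms are observed for unequal time.* Both have the same cut-off counted from start of treatment, which is the usual way to compare two regimens. The timing of IVIg and rituximab is part of each regimen, and only time after those treatments differs.
- *The PE arm loses most of its post-rituximab time.* The 4-5 day figure needs ten alternate-day sessions. The PE-arm flow chart attaches its IVIg-related PD sampling notes only to Days 6, 8 and 11. This suggests, without stating it, that IVIg was expected by about Day 11. That fits five or ten daily sessions, or five on alternate days, with a shortfall of 1 to 6 days.
- *AEs after the co-treatments are over-represented in the imlifidase arm.* The documents do not establish this. Imlifidase-arm patients who need PE also receive IVIg later (Protocol 5.3).
- *Late non-serious AEs cannot be compared.* With 30 patients and listings ordered by treatment group (SAP 4.1.1), they can be counted by hand.

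All of this stands and narrows the point to one of presentation. It does not explain why a secondary endpoint collected to Day 180 has no table of non-serious events after Day 29.

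**Conclusion.** The point holds in limited form. The Day 29 window is correct for imlifidase exposure, but it is the only basis for the AE tables. About 151 of 180 days (84%) therefore have no planned comparison by arm beyond the all-SAE tables.

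The imbalance in time after IVIg and rituximab is secondary. It is about 1 to 6 days with daily PE under the 5-day rituximab gap, larger if sessions are spaced out, and absent for five daily sessions under SAP Table 3's timing. Its size rests on an assumed PE interval.

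Two wording gaps go with this. The window's start is not literally defined in the PE arm, because it is tied to a product that PE is said not to be. The all-SAE tables also depart from the protocol's restriction, and SAP section 5 does not list that departure.

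This is a cheap improvement, not a flaw in the trial's main result.

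**What to change.** - In SAP 4.7.1 and section 8, add summary tables by SOC and PT, by intensity and by causality for all AEs from first study treatment (imlifidase infusion or first PE session) to Day 180, by arm, on the safety set.
- Keep the Day 29 treatment-emergent tables. State that their window opens at the first PE session in the PE arm.
- In SAP section 5, record that these tables, and the existing all-SAE tables, go beyond the restriction in Protocol 12.3.13.
- Reconcile the rituximab timing in SAP Table 3 with the 5 days given elsewhere in both documents.

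The cost is two or three extra tables from AE data already collected, plus a few sentences. The downside is longer output. The Day 29 tables will still carry the difference in time after the co-treatments; the added tables reduce it without removing it entirely.
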